9 STATISTICAL CONSIDERATIONS

9.1 Statistical Hypothesis

For NL-201 monotherapy (Parts 1 and 2), no statistical hypothesis will be tested during dose escalation in Part 1. In Part 2, the null hypothesis that the response rate to NL-201 is $\leq 2.5\%$ in each cohort will be tested against the alternative hypothesis that the response rate is $\geq 15\%$.

For NL-201 in combination with pembrolizumab (Parts 3 and 4), no statistical hypothesis will be tested during dose escalation in Part 3 and dose expansion in Part 4.

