9.2 Sample Size Determination

In Part 1, 2 NL-201 monotherapy dosing schedules (IV Schedule A, IV Schedule B) will be evaluated with the goal being to determine the MTD of each schedule. The MTD is defined as the highest dose for which the probability of a patient experiencing a DLT with NL-201 is $\leq 33\%$. Based on the totality of data arising in Part 1, the DMC will determine a RP2D and treatment schedule of NL-201 for Part 2 that will not exceed the MTD.

Dose escalation in Part 1 will be guided by an mTPI design with up to approximately 50 enrolled per schedule as depicted in [Figure 5](#). This design and number of patients per schedule provides a high likelihood of correctly identifying the MTD with approximately one half of the patients (ie, approximately $n = 15$) being exposed to the MTD, very few being exposed to lower, less effective doses and relatively few being exposed to the MTD+1 dose.

In addition, there will be backfill cohorts (up to approximately 12 patients in total), at certain DMC-cleared dose levels and schedules, to collect, pharmacokinetic, pharmacodynamic and response data in certain tumor types or to explore additional pre-medication regimens (eg. steroids). The decision to enroll patients into backfill cohorts and to define the patients to be enrolled will be made by the Sponsor.

Note: “Enrolled” means any patient that has met all of the study inclusion and exclusion criteria and is eligible to receive study drug.

In Part 2, an expansion cohort study will evaluate safety and estimate antitumor activity of NL-201 as a monotherapy at the RP2D in 2 cohorts of patients: (1) melanoma and (2) RCC. A Simon’s 2-stage design will be used for each cohort independently to test the null hypothesis that the true monotherapy response rate is $\leq 2.5\%$ vs the alternative that the true response rate is $\geq 15\%$. In the first stage, 18 patients will be evaluated. If 0/18 objective responses are seen, recruitment to the cohort will be stopped for futility. Otherwise, a further 12 patients will be evaluated for a total of 30 patients. This design provides 80% power and a Type I error rate of 0.031 under the stated null and alternative hypotheses.

In Part 3, with the mTPI study design, the exact number of patients needed to complete the dose escalation is unknown because it depends on the number of cohorts required to reach MTD and the number of patients in each cohort. Dose escalation will be conducted in up to 42 adult

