9.4 Statistical Analyses

9.4.1 General Considerations

Demographic data and disease-related characteristics will be summarized separately for Part 1, by schedule (eg, IV Schedule A, IV Schedule B), and Part 2, by expansion cohort. Descriptive statistics (count and percent, mean, median, standard deviation, minimum, maximum) will be used. All patient data, efficacy and safety data will be summarized. Data from Parts 3 and 4 (NL-201 in combination with pembrolizumab) will be summarized in a similar manner.

A full Statistical Analysis Plan will be prepared to describe in full the statistical methods and analyses to be applied to the data arising in this study.

9.4.2 Determination of MTD in Part 1 and Part 3

For each schedule (IV Schedule A, IV Schedule B) in Part 1 (NL-201 monotherapy), the determination of MTD will be the highest dose for which the probability of a patient experiencing a DLT with NL-201 during Cycle 1 is $\leq 33\%$. Refer to [Section 9.2](#) for more details.

Similarly, for each schedule separately in Part 3 (NL-201 in combination with pembrolizumab), the determination of MTD will be the highest dose for which the probability of a patient experiencing a DLT with NL-201 during Cycle 1 is $\leq 33\%$. Refer to [Section 9.2](#) for more details.

9.4.3 Assessment of Preliminary Efficacy in Part 2 and Part 4

For NL-201 monotherapy, while tumor response data based on both RECIST 1.1 and iRECIST will be collected from all patients in dose escalation and expansion, formal analysis of tumor response will only be performed for the expansion cohorts in Part 2 based on iRECIST. Results will be presented and summarized using an exact 95% binomial confidence interval.

Other response-related efficacy parameters including time to response, duration of response, and clinical benefit rate will be also summarized by Part 2 expansion cohort.

In expansion cohorts in Part 2, OS and progression free survival (defined as the time from study entry to the time of disease progression or death from any cause) will be displayed graphically using Kaplan-Meier plots. Median PFS and OS will be extracted from the Kaplan-Meier plots along with their associated 95% confidence intervals. PFS and OS rates at 3 monthly intervals will also be extracted. Patients who do not experience progression or death will be censored at their last clinic visit contact for the assessment of disease progression.

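### Part 2 plans a Simon two-stage test with no final rejection count, and 9.4.3 gives only an exact 95% interval, so the plan gives no determinate conclusion at 3 responses in 30

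*Combined protocol and SAP*

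**What the plan says.** Section 9.1 says that in each Part 2 cohort a null response rate of at most 2.5% will be tested against an alternative of at least 15%. Section 9.2 names the method: "A Simon’s 2-stage design will be used for each cohort independently to test the null hypothesis". It then sets the stages: "In the first stage, 18 patients will be evaluated", a cohort with no response among those 18 stops for futility, and any other cohort adds 12 patients to reach 30. The stated properties are: "This design provides 80% power and a Type I error rate of 0.031 under the stated null and alternative hypotheses". Neither section says how many responses among 30 reject the null.

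Section 9.4.3 covers the analysis. It limits the formal analysis of monotherapy tumor response to the Part 2 cohorts, based on iRECIST, and says: "Results will be presented and summarized using an exact 95% binomial confidence interval". It mentions no Simon test, cut-off, p-value or decision rule. It does not say whether the interval is two-sided, which exact method is meant, or whether the two stages are taken into account. The only exact method named in the protocol is Clopper-Pearson, under Table 14, which concerns Part 4. Section 9.4.1 defers full methods to a separate SAP.

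**The concern.** A test is sized in one place and an interval is specified in another, and nothing connects them. The test is one-sided by the form of its hypotheses. A two-sided 95% interval puts 2.5% in its lower tail, which is a stricter criterion than a rule whose type I error is between 3% and 4%. For some response counts the two could disagree about whether 2.5% has been ruled out, and without a final cut-off the protocol cannot settle it.

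What is at stake is the Part 2 conclusion for melanoma and for RCC. In an open-label study with no fixed cut-off, a borderline count could be read either way once the result is known. The power and error rate stated in 9.2 also cannot be attached to any rule, because the rule is not given.

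**Working it through.** **Inputs.** From 9.1 and 9.2: p0 = 0.025, p1 = 0.15, stage 1 n = 18, stop at 0/18, total n = 30, stated power 80%, stated type I error 0.031. From 9.4.3: exact 95% interval. Assumed: the interval is two-sided Clopper-Pearson on 30 patients.

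**1. The plan's own figure.** For a final cut-off of r responses,

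P(reject | p) = Σ over x = 1..18 of Bin(x; 18, p) × P(Bin(12, p) ≥ r − x).

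Equivalently, this is P(Bin(30, p) ≥ r) − P(0/18) × P(Bin(12, p) ≥ r), since the stop removes only cohorts with no response in stage 1.

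- r = 3, p = 0.025: 0.03839 − 0.63399 × 0.00290 = 0.0366
- r = 3, p = 0.15: 0.84860 − 0.05365 × 0.26418 = 0.8344
- r = 4, p = 0.025: 0.006368 − 0.63399 × 0.000165 = 0.0063
- r = 4, p = 0.15: 0.67834 − 0.05365 × 0.09221 = 0.6734

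| Reject at | Type I error (2.5%) | Power (15%) |
|---|---|---|
| ≥ 2/30 | 0.150 | 92.2% |
| ≥ 3/30 | 0.0366 | 83.4% |
| ≥ 4/30 | 0.0063 | 67.3% |
| Stated in 9.2 | 0.031 | 80% |

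No cut-off at n = 30 reproduces the stated pair. A design of 18 then 28 patients rejecting at 3 or more gives 0.0311 and 80.3%. The printed figures may come from a total of 28, but that is an inference.

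**2. The interval.** The 95% Clopper-Pearson lower limit is the 0.025 quantile of Beta(x, 31 − x), and the upper limit is the 0.975 quantile of Beta(x + 1, 30 − x).

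- 3/30: 2.11% to 26.5%, which contains 2.5%
- 4/30: 3.76% to 30.7%, which excludes 2.5%

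Deciding from this interval is therefore the ≥ 4/30 row of the table.

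**3. Side by side at 3/30.** The two-stage p-value for 3 or more responses is 0.0366. A Simon test with cut-off 3 rejects, while the 95% interval contains the null. Adjusting the lower limit for the two stages does not remove the conflict, because it moves only from 2.11% to 2.15%.

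**4. How often this count occurs.** P(exactly 3/30 after continuing) is the difference between the r = 3 and r = 4 probabilities.

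- True rate 15%: 0.8344 − 0.6734 = 0.161 per cohort
- True rate 10%: 0.5720 − 0.3487 = 0.223 per cohort

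**5. Size of the difference between the rules.** At a true 15%, 83.4% − 67.3% = 16.1 points of power.

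**The case against.** A reader might infer that the interval is the only response analysis planned, and that Part 2 therefore has 67% power instead of 80%. The documents do not support that. Sections 9.1 and 9.2 say that the null will be tested with the Simon design, and 9.4.3 merely fails to repeat it. Its wording is that of presentation and summary, and nowhere is the interval made the decision rule. As a summary, it leaves the power of the Simon test unchanged. Nor is 80% the right baseline, since it does not reproduce for 18 then 30.

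The 4/30 threshold also depends on method. An interval that inverts the exact two-sided binomial test is exact too. Its lower limit at 3/30 is 2.78%, which excludes 2.5%. Clopper-Pearson is the natural reading only because it is the one exact method the protocol names.

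The final cut-off of 3 is itself inferred. The p-value at 3/30 (0.037) exceeds the printed 0.031, so someone holding to 0.031 as a ceiling would not reject there. That rule would then have 67.3% power, well short of the stated 80%.

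It is also tempting to say that the interval is too wide because it ignores the two stages. Its coverage of 98.4% to 99.4% comes almost entirely from the discreteness of Clopper-Pearson. A single-stage sample of 30 gives nearly the same values.

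Finally, response is a secondary endpoint in a Phase 1 study, the only action tied to a response count is the stop at 0/18, and a fuller SAP is promised. These points limit the consequences. They do not supply the cut-off, which defines the test whose power 9.2 claims and should be fixed before data are seen.

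**Conclusion.** The point holds as a gap between sections, not as a demonstrated loss of power. The protocol plans a test without a rejection count and describes an interval without saying what it is for. At 3/30, which has probability 16% per cohort at a true 15% and 22% at a true 10%, the conclusion depends on which section is followed. The candidate rules differ by 16 points of power (83.4% against 67.3%) and about sixfold in type I error (0.0366 against 0.0063). The stated 80% and 0.031 belong to neither.

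Two assumptions carry this: that the Simon test would reject at 3 or more, and that the interval is two-sided Clopper-Pearson. The 67% applies only if that interval decides. That the stated pair fits no cut-off at n = 30 needs neither assumption. This should be corrected, but it does not undermine the design.

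**What to change.** In 9.2 and 9.4.3, state that the Part 2 hypothesis is decided by the Simon rule: stop at 0/18, otherwise reject the 2.5% null at 3 or more responses among 30. Restate the properties for 30 patients as type I error 0.037 and power 83%. In 9.4.3, name the interval method and label the 95% interval descriptive and not the decision criterion.

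If the sponsor would rather decide from the 95% Clopper-Pearson interval, 9.2 should state rejection at 4 or more of 30, about 67% power and type I error 0.006.

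A 90% interval (Clopper-Pearson 2.78% to 23.9% at 3/30, agreeing with a cut-off of 3) or a stage-adjusted interval is optional. Part 4 has no hypothesis test and needs no change.

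The cost is wording in two sections and the SAP, with no added patients or procedures. The one drawback is that the restated type I error is above the printed 0.031 or, under the alternative, the restated power is below the printed 80%.

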9.4.4 Pharmacokinetics

The PK concentrations and summary parameters of NL-201 will be listed, summarized and displayed graphically by schedules in Part 1 and the 2 expansion cohorts in Part 2.

Individual and mean serum concentration data will be plotted over time. Descriptive statistics will be presented for serum PK parameters including (but not limited to) C_{max} , t_{max} , AUC_t , AUC_{inf} , $t_{1/2}$, CL, volume of distribution (Vd), etc.

PK data collected in this study are intended to additionally contribute to population PK modeling. These models may be used to predict NL-201 PK in different dosing scenarios to further support the selection of a RP2D of NL-201. The population PK analyses may include data collected in additional NL-201 clinical studies. The analysis plan for population PK modeling will be separately developed and the results of such modeling will not be presented in the clinical study report for this study but will be presented in a separate report.

The PK data from Parts 3 and 4 will be summarized similarly.

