4.3 Justification for Dose

Part 1: NL-201 IV Monotherapy Dose Escalation

The FIH starting dose was selected based on evaluation of the totality of the nonclinical data including *in vitro* evaluation of PDn effects in human peripheral blood mononuclear cells (PBMCs), the most sensitive assay, and *in vivo* toxicity data in monkeys, the most sensitive species. The proposed starting dose of 0.1 µg/kg is predicted to result in an *in vivo* C_{max} in patients of approximately 2 ng/mL. The proposed dose is anticipated to approximate the lowest pharmacologically active dose (PAD) based on *in vitro* PDn evaluations and is 150- to 300-fold below the C_{max} achieved in monkeys given 11.44 µg/kg NL-201; a dose considered to be the NOAEL (see [Table 8](#) for dose escalation scheme).

Part 2: NL-201 Monotherapy Dose Expansion

The recommended monotherapy dose and schedule of NL-201 that is determined during dose escalation will be used during monotherapy dose expansion (Part 1). The DMC will determine this dose and schedule by considering the PK, PDn, tolerability, antitumor activity, and the occurrence of any cumulative toxicities over multiple cycles of NL-201. No randomization or dose escalation will occur, though dose reduction or delay for toxicity will be allowed.

Part 3: NL-201 in Combination with Pembrolizumab Dose Escalation

The planned dose of pembrolizumab for this study is 200 mg every 3 weeks (Q3W). Based on the totality of data generated in the Keytruda development program, 200 mg Q3W is an appropriate dose of pembrolizumab for adults across all indications. As outlined below, this dose is justified by:

- Clinical data from 8 randomized studies in melanoma and NSCLC indications demonstrating flat dose- and exposure-efficacy relationships from 2 mg/kg Q3W to 10 mg/kg every 2 weeks (Q2W) representing an approximate 5- to 7.5-fold exposure range (refer to the Investigator's Brochure)
- Population PK analysis showing that both fixed dosing and weight-based dosing provides similar control of PK variability with considerable overlap in the distributions of exposures, supporting suitability of 200 mg Q3W
- Clinical data showing meaningful improvement in benefit-risk including overall survival (OS) at 200 mg Q3W across multiple indications, and
- Pharmacology data showing full target saturation in both systemic circulation (inferred from PK data) and tumor (inferred from physiologically-based PK [PBPK] analysis) at 200 mg Q3W.

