Planned NL-201 Dose Levels^b			
1A	1B	0.1	10
2A	2B	0.3	30
3A	3B	1.0	100
4A	4B	3.0	300
5A	5B	6.0	600
6A	6B	12.0	1200
Potential NL-201 Intermediate Dose Levels^b			
2A-1	2B-1	0.6	60
3A-1	3B-1	1.5	150
3A-2	3B-2	2.0	200
4A-1	4B-1	4.0	400
4A-2	4B-2	5.0	500
5A-1	5B-1	7.5	750
5A-2	5B-2	9.0	900
5A-3	5B-3	10.0	1000

D = day; DMC = Data Monitoring Committee; IV = intravenous.

a Applicable to patients that weigh ≥ 100 kg (dose is capped as to not allow > 100 times the current dose level to be administered to a patient at 1 time).

b At the recommendation of the DMC or based on Sponsor's determination, additional dose levels may be tested and/or cohorts may be expanded.

The maximum tolerated dose (MTD) is defined as the highest dose for which the probability of a patient experiencing a DLT with NL-201 during Cycle 1 is $\leq 33\%$. At the discretion of the DMC, and in keeping with the pre-specified mTPI design matrix, additional dose levels may be tested to determine the MTD.

Based on review of DLTs, the DMC may initiate step-dosing to improve the tolerability of NL-201, wherein 1 or more step-doses below the target dose would be provided prior to reaching the target dose (see Section 6.2.1.4). If step-dosing is used, the DLT window would extend from the first dose to 21 days after receiving the target dose (ie, would include the initial reduced-dose cycles in addition to the first target-dose cycle). Once a patient receives the intended target dose for their cohort, subsequent doses for that patient will continue at that dose level unless a delay in dosing of > 6 weeks causes washout of the drug, in which case the step-dosing regimen would be repeated if the patient is to resume dosing.

Supported by the mTPI design, the DMC will determine the RP2D and treatment schedule (IV Schedule A, IV Schedule B) for Part 2 by considering the PK, PDn, tolerability, antitumor activity, and the occurrence of any cumulative toxicities over multiple cycles of NL-201.

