9.4.6 Safety Data

Safety data will be summarized for the safety evaluable population for Part 1 by schedule (eg, IV Schedule A, IV Schedule B), and Part 2; a summary will also be made by dose/schedule combining safety data from all parts of the study as appropriate. These data will include AEs and laboratory parameters. Adverse event terms will be coded using the Medical Dictionary for Drug Regulatory Activities (MedDRA[®], version 23.0 or later). Adverse events will be summarized by body system, preferred term, severity, and relationship to treatment, with procedure-related events from Screening summarized separately from treatment-emergent AE. Serious adverse events, deaths, and AEs leading to early discontinuation of study drug will be summarized. Laboratory parameters will be summarized by maximum National Cancer Institute CTCAE severity grade and also by change from study entry to scheduled time points using descriptive statistics. Laboratory parameter listings will include the normal ranges for each parameter. Each value will be classified as falling above, below, or within the normal range.

Safety data from Parts 3 and 4 will be summarized similarly, with further details to be provided in Statistical Analysis Plan.

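### Section 9.4.4 groups Part 1 PK by schedule only, so mean concentrations, Cmax and AUC would mix dose levels up to 120-fold apart

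*Combined protocol and SAP*

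**What the plan says.** For Part 1, Section 9.4.4 gives a single grouping: PK concentrations and summary parameters "will be listed, summarized and displayed graphically by schedules in Part 1 and the 2 expansion cohorts in Part 2". On mean profiles it adds: "Individual and mean serum concentration data will be plotted over time". Descriptive statistics are planned for Cmax, tmax, AUCt, AUCinf, half-life, clearance (CL) and volume of distribution (Vd). Parts 3 and 4 are to be summarised in the same way. No section plans a PK summary by dose level.

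Section 9.4.6 treats safety differently. After a summary by schedule it states that "a summary will also be made by dose/schedule combining safety data from all parts of the study as appropriate".

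Table 8 in Section 6.2.1.1 gives each Part 1 schedule six planned levels, from 0.1 µg/kg up to the row "6A 6B 12.0 1200", with possible intermediate levels in between. Table 9 in Section 6.2.1.2 starts Part 3 at 0.3 µg/kg and ends at 12. Under Section 6.2.1.1, the DMC sets the RP2D and schedule "by considering the PK, PDn, tolerability, antitumor activity, and the occurrence of any cumulative toxicities over multiple cycles of NL-201".

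**The concern.** Concentrations, Cmax and AUC depend directly on dose. A mean of them over a whole escalation schedule reflects how many patients happened to be treated at each level and describes no dose that anyone received. Its standard deviation is likewise mostly the spread of the doses.

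The contrast with Section 9.4.6 suggests that grouping by schedule and grouping by dose and schedule are two different things to the authors. Safety gets both, while PK gets only the first.

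Schedule also fails to identify what a patient received. Section 6.2.1.1 permits intrasubject escalation in Part 1. Step-dosing (Section 6.2.1.4) takes one patient through several levels, and in its first cycle Schedule A patients are dosed on Days 1 and 8. Section 6.2.2.1 allows reductions. Section 9.4.4 has no rule linking a PK profile to the dose given.

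PK characterisation is a secondary objective and one of the inputs to the RP2D, so the PK tables in the study report should be readable by dose.

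**Working it through.** The plan states no figure for this point, so there is none to reproduce. The inputs are the planned levels in Tables 8 and 9, the predicted Cmax at the 0.1 µg/kg starting dose, "in patients of approximately 2 ng/mL" (Section 4.3), and the expectation in Section 9.2 that about half the patients will be treated at the MTD.

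**Dose range.** Part 1: 12.0 / 0.1 = 120-fold. Part 3: 12 / 0.3 = 40-fold. Intermediate levels lie inside these ranges. If Part 1 escalation stops at 3.0 or 6.0 µg/kg, the range is 30-fold or 60-fold.

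**CV from the dose mix alone.** Assume exposure proportional to dose and no variation between patients. With weight w on dose d, mean m = Σwd, variance = Σwd² − m², and CV = √variance / m. In the last four rows, half the patients are at the MTD and the rest are split equally over the other levels used (my assumption).

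| Allocation | m | Σwd² | Variance | CV |
|---|---|---|---|---|
| Part 1, equal over 0.1, 0.3, 1, 3, 6, 12 | 22.4/6 = 3.733 | 190.1/6 = 31.683 | 17.746 | 113% |
| MTD 12, six levels | 7.04 | 76.61 | 27.05 | 74% |
| MTD 6, six levels | 4.64 | 33.41 | 11.88 | 74% |
| MTD 3, escalation ends at 6 | 2.425 | 9.1375 | 3.257 | 74% |
| MTD 3, six levels | 3.44 | 22.61 | 10.776 | 95% |

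Using the sample SD in the first row multiplies the CV by √(6/5), giving 124%. The Part 1 span is therefore roughly 74% to 124%. For Part 3 with equal numbers at 0.3, 1, 3, 6 and 12: m = 22.3/5 = 4.46, Σwd² = 190.09/5 = 38.018, variance 18.126, CV 95%, or 107% with the sample SD (× √(5/4)). Both lie inside that span.

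**In concentration units.** Scaling 2 ng/mL at 0.1 µg/kg in proportion gives Cmax of 2, 6, 20, 60, 120 and 240 ng/mL. With equal numbers the pooled mean is 448/6 = 74.7 ng/mL. That is 37 times the lowest level's value and 0.31 times the highest's. The top level supplies 240/448 = 54% of the sum.

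**Adding between-patient variation.** With an assumed within-level CV c, pooled CV² = (1 + c²)(31.683 / 3.733²) − 1 under equal allocation. This gives 122% for c = 30% and 136% for c = 50%. Summaries by dose level within schedule would show the 30% or 50% itself.

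**The case against.** The strongest reply is that Section 9.4.4 omits dose level but does not rule it out. Grouping by schedule is also the stratum named for demographics (Section 9.4.1) and exploratory analyses (Section 9.4.5), so it may be shorthand. Section 9.4.1 defers full methods to an SAP still to be written. The dose/schedule summary in Section 9.4.6 is attached to data combined from all parts, which makes it a weaker contrast than it first appears. All this stands, and it is why the point is minor. But the SAP will be written from a section that names one grouping, and that grouping is the wrong one for Cmax and AUC.

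A reader might infer more than the documents support:

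- **That dose proportionality could not be judged in this trial.** It could. Concentrations and parameters are listed, individual profiles are plotted, exact dosing and sampling times are recorded (Section 8.6), and population PK modelling is planned. However, those modelling results are to be reported outside the clinical study report, so its own tables still need to be readable by dose.
- **That the RP2D decision would rest on pooled tables.** No section says the DMC will use the Section 9.4.4 summaries, and population PK is named as further support for RP2D selection.
- **That every pooled PK summary is meaningless.** CL, Vd, half-life and tmax may be poolable if PK is linear. The problem concerns concentrations, Cmax and AUC.
- **That Part 4 shares the fault.** It uses one dose and schedule chosen in Part 3, with no escalation (Section 4.3).

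**Conclusion.** The point holds as a minor correction. As worded, Section 9.4.4 would average concentrations, Cmax and AUC over planned doses up to 120-fold apart in Part 1 and 40-fold in Part 3. Those summaries would describe no dose level and could not support a choice between doses.

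The CV of roughly 74% to 124% rests on dose-proportional PK and ignores between-patient variation. The upper end, 113% to 124%, needs equal numbers at all six levels and should not be read as the expected value; with half the patients at the MTD, as Section 9.2 anticipates, it is about 74% to 95%. The full ranges are planned maxima from tables headed as sample schemes and will be narrower if escalation stops early. No data are lost, so the gap lies in the planned summaries and mean plots.

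**What to change.** Amend Section 9.4.4, and carry it into the SAP, so that PK in Parts 1 and 3 is summarised and plotted by schedule, dose level actually received and cycle/day. Using the dose actually received also covers step-dosing, intrasubject escalation and dose reductions.

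Allow pooling across doses only for dose-normalised Cmax and AUC, or for parameters expected not to depend on dose (CL, Vd, half-life, tmax), and only after each has been checked by dose. A power-model assessment of proportionality is optional, since the stated objective is to characterise PK.

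The cost is a wording change and more table columns, many with few patients; listing individual values beside the summaries deals with the smallest cells. No extra sampling is needed.
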